**Type/design of trial:**

A randomized, double-blind, placebo-controlled, cross-over design will be implemented.

**Method to minimize bias:**

Participants will be randomly assigned by a computer-generated code.

**Number of study arms and intervention duration:**

Participants will be randomized to a placebo or salt treatment arm for two weeks (Period 1), followed by a wash-out period for three-weeks, ending with a cross-over to the alternative treatment arm for two weeks (Period 2). The total length of participation is 7 weeks (Figure 1).

**Name of study intervention:**

Sodium Chloride

**4.2 SCIENTIFIC RATIONALE FOR STUDY DESIGN**

The study is testing the hypothesis that a modest increase in dietary sodium intake is sufficient to change the gut microbiome and trigger alterations in the blood transcriptome that may mediate the resultant in the well described salt-sensitive changes in vascular function, epigenome, transcriptome and blood pressure observed in African Americans. The study design as a randomized, double-blind, placebo-control cross-over design enables each participant to serve as her/his own control in response to the dietary salt intervention. The cross-over design allows for an intervening ‘wash-out’ period to ensure that the participant’s diet and sodium homeostasis returns to baseline. The design’s use of each participant as her/his own control reduces the impact of inter-individual variability in the basal dietary habits and microbiome; and optimizes statistical power to detect differences in baseline blood transcriptome gene expression profiles and gut microbiome in response to the dietary intervention. Our previous studies of the human transcriptome indicate that the current design is very robust to detect changes in gene expression by DNA methylation, RNA-seq and vascular function. The randomization ensures that the sequence order of the intervention (placebo vs salt tablets) is due to chance and avoids a systematic ‘contamination’ or carryover effect of the active treatment. The double-blind administration of tasteless capsules ensures that neither the participant or research staff are aware that there could be an increased ingestion of dietary salt. The dose of sodium chloride in the capsule has previously been shown to affect biomarkers sensitive to salt balance such as measures of the renin-angiotensin-aldosterone system and blood pressure. The daily dose of sodium chloride tablets given in the protocol falls well within the wide variance of ‘normal’,

safe, intake in various cultures around the world. The increment in salt intake beyond the participant's usual diet is equivalent to eating 1-2 bowls of soup and is a dose commonly administered to treat orthostatic hypotension in patients who suffer from this disorder. It should be noted that the protocol focuses on normotensive volunteers and excludes patients with hypertension or heart failure for whom a transient increase in dietary sodium could pose a risk. We will assess, gut, skin and saliva microbiome. The oral cavity is an excellent source of easy-to-access biological material for studies of oral microbiome. This is due to the quick, non-invasive and low-cost collection. The most used source of oral samples is saliva (collected by passive drool or spit). The collection of the skin microbiome samples is commonly performed using the swabbing method. The sampling for skin microbiome was guided by the aim to consider two of the three skin microenvironments types: Sebaceous and moist microenvironments. For the first, the Retroarticular Crease was chosen and for the latter, the Antecubital Fossa was selected. These sites provide also the advantage of being relatively less exposed than dry sites such as the forearm and hence less likely to have the external environment microbiome over-represented.

The oral samples are not collected to investigate gut microbiome but rather to evaluate changes in oral microbiome with respect to changes in sodium intake. The aim is to find out if changes in sodium intake are correlated with microbiome changes in the oral cavity, in the gut and on the skin. Each site is considered separately first and then patterns of changes between sites are considered.

#### **4.3 JUSTIFICATION FOR DOSE**

Sodium chloride (1gm/capsule) and placebo will be dispensed by the NIH Pharmacy. Participant would be instructed to take 3 pills per day for a total of 3 grams. The dosing of three grams of sodium chloride per day was selected because it is sufficiently higher than normal dietary intake necessary to affect the outcome parameters and doesn't pose any health dangers. This dosage is the standard amount used in such protocol.

### **5 STUDY POPULATION**

#### **5.1 INCLUSION CRITERIA**

African American men and women who are former GENE-FORECAST participants between 21 and 65 years of age.  This criterion is inclusive of self-identified AA of both Hispanic, Latino and non-Hispanic, Latino ethnicities. Normotensive participants with systolic blood pressure (SBP) <140 mm Hg and diastolic blood pressure (DBP) <90 mm Hg and the absence of a history of prior diagnosis of hypertension.

- Willingness and ability to participate in study procedures.

#### **5.2 EXCLUSION CRITERIA**

- Individuals who are pregnant or breast-feeding.
- Individuals with high blood pressure or a history of hypertension.
- Individuals with a history of myocardial infarction, stroke, heart failure, diabetes, chronic liver or kidney diseases.
- Individuals who are taking antihypertensive, antidepressants, antidiabetic and antibiotic medications.
- Individuals currently participating in another NIH protocol.
- Individuals unable to provide informed consent.

### **5.3 INCLUSION OF VULNERABLE PARTICIPANTS**

The study will not involve vulnerable groups other than NIH employees who volunteer for participation in study. NIH employees will be provided requisite information according to OHSRP Policy 404 prior to agreeing to participate in study.

### **5.4 LIFESTYLE CONSIDERATIONS**

During the study, participants are asked to:

- Reframe from taking antibiotics. Taking such mediation will result in early withdrawal.

### **5.5 SCREEN FAILURES**

All Participants will go through screening activites after the consent has been signed. Females will undergo a pregnancy test. Participants who consent to participate in the trial and subsequently have a positive pregnancy test prior to randomization will be considered a screen failure and not enrolled in the study. Participants who consent to participate but present with systolic blood pressure (SBP) >140 mm Hg and diastolic blood pressure (DBP) >90 mm Hg at physical examination will also be considered a screen failure.

Screen failures are defined as participants who consent to participate in the study but are not subsequently assigned to the study intervention or enter the study. A minimal set of screen failure information is required to ensure transparent reporting of screen failure participants to meet the Consolidated Standards of Reporting Trials (CONSORT), publishing requirements and respond to queries from regulatory authorities. Minimum information will include demography, screen failure details, eligibility criteria, and any serious adverse event (SAE).

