**Visit to the NIH Clinical Center:**

Once potential participant arrives at the Clinical Center, they will report to admissions and be greeted by the GENE-FORECAST-SIT staff who will escort him/her to a private room to administer informed consent and baseline questionnaires. GENE-FORECAST-SIT staff (Research Nurse/Physician Assistant) will subsequently escort potential participant to phlebotomy followed by the collection of microbiome specimens from the GENE-FORECAST-SIT staff. A physical examination by the Physician Assistant will be performed on the participant, they will then have a standard physical exam, including blood pressure measurement and vitals concluding with administration of vascular function tests using Endo-PAT and SphygmoCor by the Physician Assistant. Two blood pressure measurements will be obtained from the participant by the Clinical Center Nursing Staff and an average recorded. The blood pressure will be measured using a Dinamap and will be obtained from the left arm after 5 minutes of rest with the participant in a sitting position with legs uncrossed. A 24-hour diet recall will be administered by staff from the Clinical Center Nutrition Department. Taste assessment will be administered by an Associate Investigator on the study.

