### **5.6 STRATEGIES FOR RECRUITMENT AND RETENTION**

- **Target study sample:**

Participants will be recruited from those who previously participated in the GENE-FORECAST protocol. A total of 40 normotensive African American men and 21-65 years old will comprise the total sample size. We anticipate screening 150 potential participants.

- **Anticipated accrual rate:**

40

- **Source of participants:**

Former GENE-FORECAST participants.

- **Recruitment venues:**

The GENE-FORECAST-SIT staff will contact individuals to determine interest in participating in GENE-FORECAST-SIT protocol and screen for eligibility over the telephone based on self-report information.

- **How potential participants will be identified:**

A listing of former normotensive GENE-FORECAST participants will be generated, including those in the upper tertile with vascular stiffness, by the data base manager that consented for re-contact via the GENE-FORECAST protocol.

•  

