## 8 STUDY ASSESSMENTS AND PROCEDURES

### 8.1 SCREENING PROCEDURES

A listing of former normotensive GENE-Forecast participants will be generated, including those in the upper tertile with vascular stiffness, by the data base manager that consented for re-contact via the 'Call Back' protocol. The Research Nurse will contact individual to determine interest in participating in GENE-Forecast-SIT and screen via the telephone for eligibility based on self-reported health information. Participant who agree to participate in study will be scheduled for baseline clinical visit based on availability and subsequently screened again at the Clinical Center. All participants will undergo screening activities upon coming to the NIH. Female participants will undergo a pregnancy test after consent signature. Participants who consent to participate in the trial and subsequently have a positive pregnancy test prior to randomization will be considered a screen failure and not enrolled in the study.

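### The blood-pressure screen-failure rule in 5.5 requires both values to be raised, whereas the inclusion criterion in 5.1 bars a person when either value reaches its limit

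*Combined protocol and SAP*

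**What the plan says.** Section 5.1 sets the eligibility limit: "Normotensive participants with systolic blood pressure (SBP) <140 mm Hg and diastolic blood pressure (DBP) <90 mm Hg", with no prior diagnosis of hypertension. Section 5.2 excludes "Individuals with high blood pressure or a history of hypertension" but gives no number.

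Section 5.5 describes what happens after consent. Following the rule on a positive pregnancy test, it adds a second group of screen failures, found when the person is examined on site: those who "present with systolic blood pressure (SBP) >140 mm Hg and diastolic blood pressure (DBP) >90 mm Hg". Its second paragraph then defines screen failures in general as consenting people who are not assigned to the intervention or do not enter the study.

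The other places where blood pressure could be checked before dosing carry no numeric limit:

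- Section 5.6: staff "screen for eligibility over the telephone based on self-report information".
- Section 8.1: those who agree to take part are "subsequently screened again at the Clinical Center".
- Section 1.3, description of the Clinical Center visit: "Two blood pressure measurements will be obtained from the participant by the Clinical Center Nursing Staff and an average recorded".

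**The concern.** To be eligible under 5.1, both values must be below their limits. The opposite of that is at least one value at or above its limit. Section 5.5 instead asks for both values to be strictly above. It is the only sentence that puts a number beside the on-site examination, and that visit is where pressure is measured before capsules are given, because the earlier telephone screen rests on self-report.

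The safety argument in 4.2 depends on this limit. It says the protocol "excludes patients with hypertension or heart failure for whom a transient increase in dietary sodium could pose a risk". Participants take 3 g of sodium chloride a day (4.3), mild rises in blood pressure are a listed side effect (2.3.1), and people in the upper tertile of vascular stiffness are oversampled (4.1). Staff who work from 5.5 alone could pass a person at 150/80 whom 5.1 bars.

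**Working it through.** **Step 1. The two rules side by side.**

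- Ineligible under 5.1: SBP ≥140 or DBP ≥90.
- Screen failure named in 5.5: SBP >140 and DBP >90.

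**Step 2. All combinations.** Class each value as below, at or above its limit. That gives 3 × 3 = 9 combinations.

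| | DBP <90 | DBP =90 | DBP >90 |
|---|---|---|---|
| SBP <140 | eligible | missed | missed |
| SBP =140 | missed | missed | missed |
| SBP >140 | missed | missed | named in 5.5 |

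Section 5.1 makes 9 − 1 = 8 combinations ineligible. Section 5.5 names 1 of these and misses 8 − 1 = 7. Two of the seven are an isolated rise in one value (150/80, 125/95). The other five involve a value exactly at a limit (for example 140/85, 120/90, 140/90, 140/95, 160/90). Every combination that 5.5 names is also ineligible under 5.1, so the error runs in one direction only.

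**Step 3. Whole-number grid.** Take SBP 90 to 180 (91 values) and DBP 50 to 120 (71 values).

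- All pairs: 91 × 71 = 6461.
- Eligible under 5.1: 50 × 40 = 2000, so ineligible = 6461 − 2000 = 4461.
- Named by 5.5 as written: 40 × 30 = 1200.
- If only 'and' becomes 'or' and '>' stays: 6461 − 51 × 41 = 4370. The 91 pairs still missed have neither value above its limit but at least one exactly at it.
- With SBP ≥140 or DBP ≥90: 4461 of 4461.

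The grid tests the logic. It is not weighted by how often each reading occurs.

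**Step 4. How often it might matter (illustration).** The documents give no distribution of screening blood pressure, so means, SDs and correlations are assumed, with bivariate normal readings in whole mm Hg.

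Share captured = P(SBP ≥141 and DBP ≥91) / P(SBP ≥140 or DBP ≥90).

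| Assumptions | Lowest | Median | Highest |
|---|---|---|---|
| SBP mean 120–130, SD 12–15; DBP mean 75–80, SD 8–10; correlation 0.5–0.8 | 6.7% | 19.5% | 39.0% |
| Wider: SBP mean 115–130, SD 9–15; DBP mean 70–80, SD 8–10; correlation 0.4–0.85 (288 sets, 1,000,000 simulated readings each) | 0.8% | 11.2% | 43.9% |

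In the narrower range, 61% to 93% of ineligible readings fall outside 5.5. None of the 288 wider sets reaches 50% captured.

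**The case against.** The best defence is that 5.5 does not override 5.1. The word 'also' shows that the sentence is one instance and not a full list, and nothing in it makes a person at 150/80 eligible. Sections 5.1 and 5.2 remain in force, and someone turned away under 5.1 is a screen failure by the general definition in the same section, which largely answers the worry about how screen failures are counted. Section 7.2 also lets the investigator withdraw a participant found to meet an exclusion criterion. All of this stands, and it is why the finding stops short of claiming that ineligible people would be enrolled. It does not make the stated number right: withdrawal under 7.2 is discretionary and comes after the fact, and 5.5 remains the only numeric limit attached to the examination.

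The cell count can also be challenged, since five of the seven missed combinations exist only because exact ties are counted separately. Without ties there are three ineligible combinations, of which 5.5 names one and misses two, so it still misses most of them. The percentages do rest on assumptions; only their direction is stable.

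Finally, the practical reach may be small. Candidates come from a list of former normotensive participants, and the addendum (section 12) reports 28 enrolled of the 40 planned. The documents do not say that recruitment has closed.

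**Conclusion.** The point holds. Section 5.5 is wrong as written in two respects, the conjunction and the strict inequality, and it leaves 7 of 8 ineligible combinations unnamed. This follows from the text alone. That most ineligible readings are missed in practice rests on assumed distributions, but it is true in every set tried, with capture between about 1% and 44%. How many of the 150 people to be screened (5.6) would be affected cannot be derived from the documents, and it could be none. No endpoint, analysis or sample-size figure depends on it. It should be corrected because it is a safety-relevant eligibility limit in a salt-loading trial.

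**What to change.** In 5.5, replace the blood-pressure condition with: SBP ≥140 mm Hg or DBP ≥90 mm Hg at physical examination. Leave 5.1 unchanged. Every reading is then either eligible or a screen failure under both sections. Changing 'and' to 'or' alone is not enough, because 140/85, 120/90 and 140/90 would still go unnamed.

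The cost is a few words in an amendment and at most a few more screen failures, all of them people whom 5.1 already bars. The rewording helps only later screening. For those already enrolled, comparing the recorded baseline averages with 5.1 would show whether the mismatch had any effect.

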### **5.6 STRATEGIES FOR RECRUITMENT AND RETENTION**

- **Target study sample:**

Participants will be recruited from those who previously participated in the GENE-FORECAST protocol. A total of 40 normotensive African American men and 21-65 years old will comprise the total sample size. We anticipate screening 150 potential participants.

- **Anticipated accrual rate:**

40

- **Source of participants:**

Former GENE-FORECAST participants.

- **Recruitment venues:**

The GENE-FORECAST-SIT staff will contact individuals to determine interest in participating in GENE-FORECAST-SIT protocol and screen for eligibility over the telephone based on self-report information.

- **How potential participants will be identified:**

A listing of former normotensive GENE-FORECAST participants will be generated, including those in the upper tertile with vascular stiffness, by the data base manager that consented for re-contact via the GENE-FORECAST protocol.

•  
**5.6.1 Costs**

There will be no out-of-pocket cost to participants.

**5.6.2 Compensation**

Participants will receive \$50 per visit disbursed through the Research Volunteer System (RVS) for Visits 1,2, 3, and 4. A final payment for \$300 will be mailed or sent via direct deposit to the participant by the RVS at the completion of the study and recovery of the study equipment (24hr BP monitor; Smart-Bottles). The total possible compensation for participating in the completed study will be \$500. Participant will also receive a \$25 voucher for lunch each visit and be afforded a one-way pre-paid taxi trip to the NIH Clinical Center.

**6 STUDY INTERVENTION**

**6.1 STUDY INTERVENTIONS(S) ADMINISTRATION**

**6.1.1 Study Intervention Description**

There are no unapproved drugs or devices being used in this study.

Sodium Chloride is Food and Drug Administration (FDA) approved for a variety of clinical conditions and is included in a wide variety of commonly consumed processed foods.

**6.1.2 Dosing and Administration**

**Sodium Chloride and Placebo:** Sodium Chloride (1gm/capsule) and corresponding placebo will be provided by the NIH Pharmacy. Participant will be instructed to take 3 pills per day for a total of 3 grams. The dosing of three grams of sodium chloride per day was selected because it is sufficiently higher than normal dietary intake necessary to affect the outcome parameters and doesn't pose any health dangers. This dosage is the standard amount used in such protocol.

**6.1.2.1 Dose Escalation**

There will be no dose escalation. Participants will be instructed to take 3 assigned salt or placebo pills per day for a total of 3 grams.

**6.1.2.2 Dose Limiting Toxicity**

Not applicable

**6.1.2.3 Dose Modifications**

Not applicable

**6.1.2.4 Drug Administration**

Participant will be instructed to take 3 pills per day for a total of 3 grams. If one capsule is missed per day, participant should not make up the next day by taking an additional capsule.

**6.2 PREPARATION/HANDLING/STORAGE/ACCOUNTABILITY**

**6.2.1 Acquisition and Accountability**

The sodium chloride and placebo capsules will be manufactured by Pine Pharmaceuticals in Tonawanda, New York and sent directly to the NIH Clinical Center Investigational Drug & Research Section Outsourcing Unit (IDOU). The sodium chloride and placebo capsules will be subsequently sent to the NIH Clinical Center pharmacy who will be dispense directly to

participants based on randomized double-blind ID list previously provided by PI. Expired and unused product will be discarded by the IDOU and not sent back to the manufacturer.

#### **6.2.2 Formulation, Appearance, Packaging, and Labeling**

The sodium chloride and placebo capsules will be formulated by Pine Pharmaceuticals in Tonawanda, New York based on FDA guidelines. There will be no distinguishing characteristics between both capsules. The sodium chloride and placebo capsules will be put in a separate ‘smart bottle’ by Clinical Center pharmacy and labelled based on randomized double-blind participant ID list previously provided by PI with instruction to take two times a day. The smart bottle technology will electronically monitor adherence to daily treatment and is designed to remind participant to take treatment and to alert when treatment has been missed. Smart bottles will be purchased from a reputable vendor with a history of collaboration in such trials.

#### **6.2.3 Product Storage and Stability**

The product will be stored in the Clinical Center pharmacy based on protocol designed to protect from light, temperature, and humidity. The smart bottle will also be designed to protect from such elements.

#### **6.2.4 Preparation**

The Clinical Center pharmacy will dispense the sodium chloride and placebo capsules in separate smart bottles. Capsules do not involve thawing, diluting, mixing and reconstitution/preparation.

### **6.3 MEASURES TO MINIMIZE BIAS: RANDOMIZATION AND BLINDING**

A randomized, double-blind, placebo-controlled, cross-over design will be implemented (Figure 1). Participants will be randomly assigned by a computer-generated code based on study ID. All study staff will be blinded to randomization throughout the trial period. The randomized list will be provided to the Clinical Center pharmacy who will have the key to specific participant randomization.

### **6.4 STUDY INTERVENTION COMPLIANCE**

The sodium chloride and placebo capsules will be put in separate smart bottle by Clinical Center pharmacy and labelled based on randomized double-blind ID previously provided by PI instructing participant to take three times a day. The smart bottle technology will electronically monitor adherence to daily treatment and is designed to remind participant to take treatment and to alert when treatment has been missed. Smart bottles will be purchased from a reputable vendor with a history of collaboration in such trials.

The smart bottle includes an electronic interface and database that allows clinical study staff to monitor, document, and calculate compliance. We will also collect spot urine test for sodium/potassium at baseline and at the end of each treatment test as an additional measure of adherence to the dietary sodium intervention.

